## Post-Surgical Procedures

Buccal and occlusal photographs of the surgical site will be obtained. Post-operative medications will be prescribed. An intraoral PA radiograph will be taken in order to assess ridge preservation surgery.

## 3.1.4 Visit 4: Post-Operative Visit (7 days ± 2 days)

Buccal and occlusal photographs of the surgical site will be obtained. Gentle debridement and oral hygiene instruction will be provided. AEs will be recorded.

## 3.1.5 Visit 5: Post-Operative Visit (14 days ± 2 days)

Remaining suture material will be removed (only Group B). Buccal and occlusal photographs of the surgical site will be obtained. AEs will be recorded.

## 3.1.6 Visit 6: Post-Operative Visit (28 days ± 2 days)

Buccal and occlusal photographs of the surgical site will be obtained. Gentle debridement and oral hygiene instruction will be provided. AEs will be recorded.

## 3.1.7 Visit 7: Post-Operative Visit (2 months ± 4 days)

Buccal and occlusal photographs of the surgical site will be obtained. Gentle debridement and oral hygiene instruction will be provided. AEs will be recorded.

## 3.1.8 Visit 8: Post-Operative Visit (4 months ± 7 days)

In this visit, a second segmental CBCT scan will be obtained for all patients, using the same settings employed at baseline, as detailed in above. Images will provide post-ridge preservation data for horizontal and vertical bone locations. Buccal and occlusal photographs of the surgical site will be obtained. AEs will be recorded.

# 3.1.9 Visit 9: Re-entry and Dental Implant Placement (5 months ± 14 days)

## Pre-Surgical, Surgical, and Post-Surgical Care

See Section 3.1.3.

#### Pre-Surgical Procedures

Buccal and occlusal photographs of the surgical site will be obtained. Standardized periapical radiograph of a target tooth will be taken.

VERSION 1.1 11(33)

If the bucco-lingual ridge width is judged not enough for implant placement the subject will be terminated from the study and will receive an appropriate treatment and followed according to the clinic's routines.

#### Surgical Procedure

Implant placement is made per standard procedure. For patients in each treatment group, a trephine drill will be used to harvest a core of bone for descriptive histology. A trephine drill will be used to harvest a core of bone corresponding with the planned implant length. A trephine drill of 2.8 mm in diameter will be used as the first choice. If another diameter has to be used a diameter of the trephine will be recorded in CRF. A length of a trephine will be up to 8 mm. Following harvesting, the trephined bone core will immediately be transferred to a solution of 10% neutral buffered formalin (NBF). These samples are to be used for histomorphometric assessment. Bone Density Classification (Misch Classification)(10) will be evaluated and recorded in CRF.

Selection of implant system will be left to the judgment of study sites; however the same system should be used in all the cases treated at the site. Implant site preparation and placement will proceed according to the implant system manufacturer recommendations.

When one-stage approach is chosen, a healing abutment will be placed to finger tightness. Depending on the buccal soft tissue thickness, the crestal tissue will either be removed or deepithelialized and inverted to the buccal to increase the soft tissue thickness. When two-stage procedure is chosen, a cover screw will be placed and stay buried and left to heal. Once healed, a second surgery is performed to attach an abutment for securing the crown in place. Selection of approach will be left up to the dentist's discretion.

#### Post-Surgical Procedures

An intraoral periapical radiograph will be obtained immediately postoperatively to assess the depth and angulation of dental implant placement. Buccal and occlusal photographs of the surgical site will be obtained. An intraoral PA will be taken in order to assessment of implant placement. Post-surgical AEs will be recorded.

Post-operative medications will be prescribed.

## 3.1.10 Visit 10: Prosthesis Delivery

Visit 10 will be scheduled on the day of prosthesis delivery or at least 14 days after prosthesis delivery. Buccal and occlusal photographs of the surgical site will be obtained.

Standardized periapical radiograph of a study site will be taken following prosthesis was delivered. Plaque Index (modified Quegley- Hein) of teeth adjacent to the study site and

VERSION 1.1 12(33)

bleeding on probing on the study site will be evaluated and recorded in CRF. AEs will be recorded.

# 3.1.11 Visit 11: Follow-Up Visit (6 months ± 14 days after Prosthesis Delivery)

[figure not shown]
Buccal and occlusal photographs of the surgical site will be obtained. Standardized periapical radiograph of a target tooth will be taken. Standardized periapical radiograph of a study site will be taken following prosthesis was delivered. Plaque Index (modified Quegley- Hein, 1970) of teeth adjacent to the study site and bleeding on probing on the study site will be evaluated and recorded in CRF. AEs will be recorded.

# 3.1.12 Visit 12: Follow-Up Visit (12 months ± 28 days after Prosthesis Delivery)

Buccal and occlusal photographs of the surgical site will be obtained. Standardized periapical radiograph of a target tooth will be taken. Standardized periapical radiograph of a study site will be taken following prosthesis was delivered. Plaque Index (modified Quegley- Hein, 1970) of teeth adjacent to the study site and bleeding on probing on the study site will be evaluated and recorded in CRF. AEs will be recorded.

VERSION 1.1 13(33)

Figure 2 Appointment flow chart

VERSION 1.1 14(33)

Table 1 Study plan

Visit Number	1	2	3	4	5	6	7	8	9	10	11	12
Visit Description	Screeni ng	Enrolm ent	Ridge preserv ation	Post-op	Post-op	Post-op	Post-op	Post-op (CBCT)	Implant placem ent	Prosthe sis delivery	Follow- up	Follow- up
Visit Window		-2w>	0	1w±2d	2w±2d	4w±2d	2m±4d	4m±1w	5m±2w	0	6m±2w	1Y±4w
Patient Information												
Informed consent		Х										
Patient demographics	Х											
Medical/surgical history	Х											
Oral examination	Х											
Inclusion/exclusion criteria		Х										
Treatment												
Clinical photography			Х	Х	Х	Х	Х	Х	Х	Х	Х	Х
Tooth extraction / Ridge preservation			Х									
Suture removal					Х							
Trephined bone sample									Х			
Implant placement									Х			
Assessment												
CBCT (ridge dimensions)		(X) 						Х				
Standardized PA radiograph			Х						Х	Х	Х	Х
Bone density classification									Х			
Histology									Х			
Other												
Width of keratinized mucosa			Х									
Horizontal ridge width			Х									
Wound dehiscence				Х	Х	Х	Х	Х				
Adverse events/Adverse device effects			Х	Х	Х	Х	Х	Х	Х	Х	х	Х

1.Pre-existing CBCT taken for the treatment planning are available.

## 3.2 Rationale and risk/benefit assessment

It is necessary to further define the effects of different grafting materials on clinical outcomes following ridge preservation. This study will employ gold standard methods of evaluation efficacy and safety conforming to that stipulated of the medical, clinical research, and regulatory communities to demonstrate clinical benefit of GUIDOR® easy-graft CLASSIC. The study has been designed to treat a clinical scenario commonly encountered in clinical practice.

The patients will benefit from a preserved alveolar ridge dimension to permit dental implant placement. The public will benefit from the study results which will help to refine the knowledge of bone preservation and healing following ridge preservation with different grafting material. This will help aid clinicians in the selection of materials to optimize their clinical outcomes of treatment. The study also includes dental implant placement and acquisition of data that will help to define the effect that different grafting materials have on implant stability at time of placement and follow-up period for one year after the implant placement. Data acquisition includes minimally invasive collection methods, both before and after the surgical procedures.

## 3.2.1 Study selection record

Investigator(s) will keep a record of subjects who were considered for enrollment but were never enrolled (e.g., subject screening log). This information is necessary to establish that the subject population was selected without bias.

#### 3.2.2 Inclusion criteria

For inclusion in the study subjects must fulfill all of the following criteria:

- 1. Provision of informed consent
- 2. At least 18 years old
- 3. In need of one posterior tooth, excluding third molar molars, planned for extraction and replacement with a dental implant (If the subject requires two adjacent socket preservation, they can still be enrolled in the study but only one site will be used for the study)
- 4. Intact ridge as verified with cone-beam CT scan
- 5. At least one natural tooth adjacent to the study site present.

#### 3.2.3 Exclusion criteria

Any of the following is regarded as a criterion for exclusion from the study:

- 1. Insufficient interocclusal space to allow for implant supported prosthesis
- 2. Dehiscence or fenestration identified at the time of reviewing CBCT.
- 3. No previous interventions performed involving soft and/or bone grafting

- 4. Non-treated caries or uncontrolled periodontal disease present affecting the teeth in adjacent to study site
- 5. Any of natural teeth adjacent to the study site presents active periapical endodontic lesion ("active periapical endodontic lesion" will be determined per consultation by endodontics specialist).
- Adjacent tooth (mesial and distal) to study site was extracted within last 6 months
- 7. Smoker using more than 10 cigarettes or equivalent per day
- 8. Smokeless tobacco use or e-cigarette use
- 9. Current alcohol or drug abuser
- 10. Systemic or local disease or condition that would compromise post-operative healing and/or osseointegration e.g. uncontrolled diabetes
- 11. Need for systemic corticosteroids or any other medication that would influence post-operative healing and/or osseointegration
- 12. Pregnancy, as indicated by positive urine human chorionic gonadotropin (HCG) test result.
- 13. Unable or unwilling to return for follow-up visits for a period of 5 months
- 14. Unlikely to be able to comply with study procedures according to Investigators judgement
- 15. Subject in other clinical trials

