#### 3.1.2 Visit 2: Enrollment

Visit 1 (Screening) and Visit 2 (Enrollment) may occur on the same day. Individuals meeting all inclusion and none of the exclusion criteria and that have signed all appropriate consent forms will be further evaluated. Before any assessment or examination is carried out for study purposes the subject must have been informed orally and in writing about the study, and have signed the appropriate consent forms. Informed consent for the research study will be given and signed on paper, as well as

VERSION 1.1 7(33)

HIPAA authorization, if not already obtained. Subjects will also be asked to sign informed consent documents.

Subjects meeting all inclusion and none of the exclusion criteria will be randomly allocated to Group A or B. Subjects with smoking habit will be stratified to be distributed equally to two treatment groups.

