### Procedures for handling incorrect enrolled subjects

Subjects not meeting the inclusion/exclusion criteria for a study should, under no circumstances, be enrolled into the study - there can be no exceptions to this rule. When subjects not meeting the study criteria are enrolled in error, or if subjects subsequently fail to meet the criteria for the study after enrollment, they will be excluded from the study and from the analyses.

If subjects are excluded intraoperatively (e.g. dehiscence), the subjects will receive a standard grafting treatment at no cost. However, an implant placement at the site will be at the patient's cost.

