# 4 MEASUREMENTS OF STUDY VARIABLES AND DEFINITIONS OF OUTCOME VARIABLES

# 4.1 Screening and demographic measurements

The following data will be recorded via a standard CRF:

- Date of birth
- Sex
- Race
- Relevant medical and surgical history
- Medication
- Oral examination
- Local condition of alveolus and adjacent teeth
  - Periodontal disease
  - o Bone loss
  - Caries
  - Endodontic treatment
  - Existing periapical radiolucency
- Tobacco use
- Reason for tooth extraction
- Previous bone graft, soft tissue graft, or apical surgery
- Opposing tooth contact in maximum intercuspation

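### Exclusion criterion 3 has reversed polarity: as written it excludes patients without previous grafting and admits only those who have had some graft

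*Combined protocol and SAP*

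**What the plan says.** Section 3.2.3 of the protocol opens its list with "Any of the following is regarded as a criterion for exclusion from the study". Item 3 of that list is "No previous interventions performed involving soft and/or bone grafting".

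The list is applied as follows:

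- Section 3.1.2 (Visit 2): "Subjects meeting all inclusion and none of the exclusion criteria will be randomly allocated to Group A or B".
- Section 3.2.5, on incorrectly enrolled subjects: those who do not meet the criteria should "under no circumstances, be enrolled into the study - there can be no exceptions to this rule".
- The same part of section 3.2.5, on those enrolled in error or later found not to meet the criteria: "they will be excluded from the study and from the analyses".

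The only other mention of earlier grafting is in section 4.1, which lists "Previous bone graft, soft tissue graft, or apical surgery" among the items recorded at screening.

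**The concern.** A list of exclusions works by matching: a patient who fits an item is out. Item 3 is worded as something a patient ought to satisfy, so fitting it and being suitable appear to coincide, which is the opposite of how the list operates.

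This is an operative rule and not background text. It decides who may be randomized and, through section 3.2.5, who stays in the analyses. A center that follows the words recruits only people with a grafting history. A center that follows the presumed intent enrols people who match a written exclusion, under a rule that allows no exceptions. A monitor checking adherence (section 7.1) would then have to record them as violations.

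**Working it through.** The protocol states no figure on this point. The check is mainly one of reading, with one small piece of arithmetic.

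**Step 1: logic of the item.** The lead-in says to exclude if the item is true. Item 3 is true when there has been no previous grafting.

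| Patient | Matches item 3? | Result as written |
|---|---|---|
| No previous soft-tissue or bone graft | Yes | Excluded |
| Any previous soft-tissue or bone graft | No | Passes item 3 |

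**Step 2: polarity of the rest of the list.** The list has 15 items. Item 1, for example, is "Insufficient interocclusal space to allow for implant supported prosthesis", a condition that disqualifies. The remaining items follow the same pattern: bone defects on CBCT, disease of adjacent teeth, recent adjacent extraction, tobacco, substance abuse, interfering disease or medication, pregnancy, inability to attend or comply, and participation in another trial. Even the items with negative wording (13 and 14) describe a reason to exclude. So 15 − 1 = 14 items run one way, and item 3 alone runs the other.

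**Step 3: search for a correction elsewhere.**

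- The synopsis paragraph on the target population describes single posterior extraction sockets and does not mention grafting history.
- The inclusion criteria (section 3.2.2) do not mention it.
- Section 4.1 records it but does not say which answer makes a patient eligible.

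No text overrides item 3.

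**Step 4: scope.** Items 4 to 6 tie their conditions to the teeth next to the study site, and item 6 gives a window of 6 months. Item 3 gives neither a location nor a period. Literally, a graft anywhere, at any time, decides the matter.

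**Step 5: possible size.** Let *g* be the number of enrolled subjects with no previous graft. The protocol gives no frequency for this, so 0 ≤ *g* ≤ 44 is an assumption covering the whole range. If section 3.2.5 were enforced on the literal text, 44 − *g* subjects would remain before any dropout:

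- *g* = 0: 44 remain.
- *g* = 4: 40 remain, which equals the target of at least 40 evaluable subjects in section 3.1.
- *g* = 5: 39 remain, below the target.
- *g* = 44: none remain.

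The margin of 44 − 40 = 4 is already set aside for the 10% dropout, and section 6.1.3 does not replace dropouts. The power calculation in section 6.3 does not itself depend on item 3.

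**Step 6: effect on the A versus B comparison.** Eligibility is settled before allocation (section 3.1.2), and randomization is stratified by center, with 11 per group at each (section 3.4). Even if the two centers read item 3 differently, each center's population would be split between both arms in the same way.

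**The case against.** The strongest reply is that this is an obvious drafting slip. A sentence in inclusion style has landed in the exclusion list, nothing in the objectives suggests a trial of previously grafted patients, and experienced investigators would read it in the sensible direction. That is very likely true, and it means item 3 should not be read as a deliberate design choice. It does not remove the problem. The intended direction is never stated, the rule allows no exceptions, and guessing the direction still leaves site and period open.

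Three stronger readings are tempting, and the documents do not support them:

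- A reader might infer that the rule admits only previously grafted *sites*. Item 3 names no site, so its literal effect is on patients with any grafting history.
- A reader might infer that nearly all of the 44 would be ineligible. That may be plausible, but no frequency of earlier grafting is given.
- A reader might infer that different readings at the two centers would bias the treatment comparison, particularly as section 6.1.4 leaves center out of the primary model. Differing readings are conjecture, and for the reason in step 6 they would not by themselves bias A against B. They would affect whom the results describe, and possibly variability. The remaining route into the analysis is removal after enrolment under section 3.2.5, if it were enforced literally or unevenly. Nothing in the protocol indicates that either is planned.

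**Conclusion.** The point stands as an error in an operative eligibility rule. As written, item 3 either defines the wrong population or turns each graft-naive subject enrolled into a formal violation who is liable to removal from the analyses. That the population is wrong rests on the evident intent shown by the other 14 items, which the sponsor has to confirm. The number affected lies between 0 and 44 and cannot be narrowed from the documents; five or more removals would take the trial below 40 evaluable subjects even without dropout. What is at stake is the study population, adherence to the protocol and the analysis set. The validity of the randomized comparison is not directly threatened.

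**What to change.** Amend section 3.2.3 so that item 3 agrees with its lead-in, either by removing the word *No* or by moving the sentence to the inclusion criteria in section 3.2.2. In either case the sponsor should confirm the intended direction and state whether the criterion refers to the study site and over what period. Moving the sentence unchanged would leave those last two points open.

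If enrolment has begun, document how each center applied item 3, subject by subject, before anyone is excluded from the analyses under section 3.2.5.

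The cost is a short amendment, notified to or approved by each IRB before implementation as section 7.4 requires. No new data are needed to establish whether a subject had earlier grafting, because section 4.1 already records it. If a site or period is added, check that the existing screening entry holds that detail.

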### 3.2.4 Restrictions

Subjects will be advised of the following restrictions during the study period:

- Bridge or denture involving the study site is not allowed except for Essex type appliance as long as it does it does not touch the surgical site.
- To avoid disruption of wound healing during the initial study period the subject should have a restricted diet for at least 14 days (printed instructions will be distributed to the subjects at Visit 3 per institutional standard of care).
- For current smokers, no more than 10 cigarettes per day are allowed.

## 3.2.5 Discontinuation of subjects from treatment or assessment

## Criteria for discontinuation

Subjects may be discontinued from study treatment and assessments at any time. Specific reasons for discontinuing a subject from this study are:

- Voluntary discontinuation by the subject who is at any time free to discontinue his/her participation in the study, without prejudice to further treatment
- Safety reasons as judged by the investigator and/or Sponsor

VERSION 1.1 17(33)

- Severe non-compliance to protocol as judged by the investigator and/or Sponsor
- Incorrect enrolment (i.e., the subject does not meet the required inclusion/exclusion criteria for the study)
  - If a dehiscence and/or a fenestration are observed intraoperatively upon tooth extraction, the subject will be excluded.
- Subject received further dental therapy on study site or adjacent teeth without consent of investigator (e.g. new crown, periodontal surgery, or orthodontics on adjacent teeth)
- Subject lost to follow-up

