## Procedures for discontinuation

Subjects who discontinue should always be asked about the reason(s) for their discontinuation and the presence of any AEs or ADEs. If possible, they should be seen and assessed by an investigator(s). Ongoing AEs and ADEs should be followed up.

A subject will be classified as lost to follow up only if, he/she has failed to return to the required study visits and his/her dental status remains unknown, despite multiple attempts to contact the subject via telephone, fax, email, certified letter and through subject locator agencies (if allowed per national regulation).

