# 3.4 Method of assigning subjects to treatment groups

Screening numbers will be assigned at day of screening (Visit 1). Subjects at center 1 will receive numbers starting at S101 and subjects at center 2 will receive numbers starting at S201. Subject numbers (subject ID) will be consecutively allocated in series at day of inclusion (Visit 2). Subjects at center 1 will receive numbers starting

VERSION 1.1 19(33)

at 101 and subjects at center 2 will receive numbers starting at 201. Enrollment will continue until 22 subjects at each center have been allocated a subject ID. If a subject discontinues, the subject number will not be reused.

Subjects will be randomized strictly sequentially at enrollment (Visit 2). The randomization schedule will be generated using a validated system under the responsibility of the data management team. The randomization procedure will be concealed. Randomization will be stratified by center and smoking habit, i.e. each center will have 11 subjects in each group A and B, respectively with an equal number of subjects with current tobacco consumption per group. The allocation will be revealed to the clinician only following tooth extraction for ridge preservation.

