# 6.1.3 Handling of dropouts and missing data

Patients dropping out from the trial prior to study end will not be replaced. Data totally missing will not be estimated.

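### Section 3.2.5 does not separate stopping treatment from stopping assessment, so a grafted subject can lose the 4-month CBCT for reasons linked to outcome

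*Combined protocol and SAP*

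**What the plan says.** Section 3.2.5 (Criteria for discontinuation) opens with one rule for both treatment and measurement: "Subjects may be discontinued from study treatment and assessments at any time". Three of the listed reasons can arise after the graft is in place:

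- "Safety reasons as judged by the investigator and/or Sponsor";
- severe non-compliance, on the same judgement;
- "Subject received further dental therapy on study site or adjacent teeth without consent of investigator", with a new crown, periodontal surgery and orthodontics on adjacent teeth as examples.

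Under Procedures for discontinuation, "Subjects who discontinue should always be asked about the reason(s) for their discontinuation and the presence of any AEs or ADEs". They are to be examined where that can be arranged, and "Ongoing AEs and ADEs should be followed up". The procedures mention neither the CBCT nor events that begin after discontinuation.

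On allocation, Section 3.4 says: "The allocation will be revealed to the clinician only following tooth extraction for ridge preservation". On missing data, Section 6.1.3 says that dropouts are not replaced and that "Data totally missing will not be estimated".

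**The concern.** The graft is the only treatment that is randomised, and it is complete at Visit 3. Discontinuing a subject after that point cannot undo the exposure. It can only remove data.

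The reasons in Section 3.2.5 that can apply between Visit 3 and Visit 8 are not neutral with respect to outcome. A wound complication may lead to a safety decision or to treatment elsewhere, and it may plausibly go with more ridge loss. If the subject then leaves assessment, the Visit 8 scan is never taken. The masked reading in Section 4.2.1.1.1 protects the scans that exist; it cannot repair one that does not.

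Two of the three reasons rest on judgement without a stated criterion. The investigator who may exercise that judgement is the treating clinician and knows the arm. Losing the worst results from an arm makes that arm look better than it was. For safety, events that first appear after discontinuation have no stated route into the adverse event tables, whereas retained subjects are asked at every visit through Visit 12.

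**Working it through.** **1. Sequence of events.** The graft is placed at Visit 3 (Section 3.1.3). The CBCT for the primary endpoint is at Visit 8, 4 months ± 7 days (Sections 3.1.8 and 4.2.1.1.1). The discontinuation reasons above can act anywhere in between. Two other exits are separate matters: exclusion for eligibility failure (Section 3.2.5, incorrectly enrolled subjects), and termination for a narrow ridge at Visit 9 (Section 3.1.9), which comes after the CBCT. Section 6 defines no analysis set and no sensitivity analysis for a missing Visit 8 scan.

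**2. The plan's sample size.** Inputs from Section 6.3: difference 0.7 mm, SD 0.8, alpha 0.05, power 80%. Two-sided testing is from Section 6.1. By the normal approximation,

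n per arm = 2 × (1.960 + 0.842)² × (0.8 / 0.7)² = 2 × 7.85 × 1.306 ≈ 20.5, rounded up to 21.

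The stated 20 per group is reproduced within one subject; power at 20 is 0.79.

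**3. Possible bias (assumed inputs).** If k of 22 subjects in one arm have no scan, and their mean bone loss exceeds that of the retained subjects by d, the full-arm mean is the retained mean plus k × d / 22. The analysed mean is therefore off by k × d / 22. The documents give neither a complication rate nor d. I take k = 1 to 2, and d from 0.8 mm (one planning SD) to 3 mm.

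| k | d (mm) | k × d / 22 (mm) | Share of 0.7 mm |
|---|---|---|---|
| 1 | 0.8 | 0.036 | 5% |
| 2 | 0.8 | 0.073 | 10% |
| 1 | 3 | 0.136 | 19% |
| 2 | 3 | 0.273 | 39% |

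The last row needs both losses in the same arm, each with an excess of 3 / 0.8 = 3.75 planning SDs.

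**4. Power.** This is the smaller effect. The Wilcoxon column is simulated with normal data.

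| Evaluable per arm | Normal approximation | t-test | Wilcoxon |
|---|---|---|---|
| 22 | 0.827 | 0.809 | 0.795 |
| 20 | 0.790 | 0.769 | 0.752 |
| 18 | 0.747 | 0.723 | 0.692 |

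Keeping 22 rather than 20 per arm gains about 4 points. The plan already allows for 44 − 40 = 4 subjects without evaluable data (Section 3.1), but an allowance for number does nothing about which subjects are lost.

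**The case against.** The strongest reply is that Section 3.2.5 grants a permission and imposes no requirement. It says subjects may be discontinued, and the section's own heading joins treatment and assessment with *or*. A complication therefore does not remove anyone automatically, and a careful investigator could keep the subject for the scan. That is correct: the loss is possible, not certain. But nothing in the plan asks the investigator to keep the subject, and the choice lies with someone who knows the arm.

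A reader might infer that discontinued subjects lose all later safety follow-up. The documents do not support this. Discontinuing subjects are always asked about events, and ongoing events are followed, so an infection present at discontinuation is covered. Section 4.3.1.3 also requires reporting of any serious event during the study. What remains is events that first arise afterwards, mainly non-serious ones.

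A reader might also take the graft to be the only study treatment. The synopsis (Duration of treatment) places implant placement at 5 months inside the treatment period, so there is later treatment to stop. The graft is the only *randomised* treatment, and that is what the point needs.

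The off-study therapy criterion has a sound measurement reason. Sections 4.2.1.1.2 and 4.2.2.2.2 use the adjacent-tooth CEJs as landmarks, which a crown or orthodontics could alter, and the examples given concern adjacent teeth more than graft complications. This stands, and it is why such scans need a flag and a sensitivity analysis. It does not justify never taking them.

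Finally, the size depends on assumptions, and the planned Wilcoxon test limits the weight of extreme values. Both stand.

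**Conclusion.** The gap is real and worth closing. After grafting, a subject may be taken out of assessment for reasons that can be related to outcome. Nothing secures the Visit 8 CBCT or the recording of later-onset adverse events, and the missing result is simply left out. On the assumptions in the working, the affected arm's mean would shift by about 0.04 to 0.27 mm, 5% to 39% of the design difference. The lower part of that range is the more credible. The 39% figure is an extreme, and the effect on the rank-based test would be smaller than on the means; I put no figure on it.

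Two further inferences go beyond the documents. One is that the sponsor decides with knowledge of the allocation. Section 3.4 reveals it to the clinician, while the synopsis (Study design) has the key opened only after all re-entry visits, so knowledge of the arm is shown for the clinician alone. The other is that the bias would favour easy-graft. That would need more complication-related losses in Group A, and the documents give no rates for either arm.

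**What to change.** Amend Section 3.2.5 so that stopping treatment and stopping data collection are separate decisions:

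- Subjects discontinued after grafting are still asked to attend the Visit 8 CBCT and the scheduled adverse event collection, unless they withdraw consent to follow-up, are lost, or the investigator judges the procedure unsuitable for safety.
- The reason for discontinuation, and the date and reason of any off-study therapy, are recorded.
- Data obtained after such therapy stay in the primary comparison with a flag.
- Section 6 adds a sensitivity analysis that leaves out measurements taken after therapy at the site or adjacent teeth.

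Clinical management of these subjects stays with the investigator.

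The cost is a wording change and one extra analysis; the visits and the scan are already in the schedule. The downside is that some retained scans will follow off-study therapy and will not reflect the randomised graft alone, which the flag and the sensitivity analysis are there to handle.
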